## **17.0 Statistics**

As the trial is a pragmatic parallel group RCT data will be reported and presented according to the CONSORT 2010 statement (Schultz et al 2010). As a pilot/feasibility study the main analysis will be mainly descriptive and focus on confidence interval estimation and not formal hypothesis testing. We will report rates of consent, recruitment and follow-up by randomized group. Outcome measures will be summarised overall and by randomized group, to inform sample size estimation for the main trial.

## 17.1 Set up error

The set up error is defined as the deviation between the actual and expected position, calculated as a shift in the isocentric position when an image is compared against its corresponding reference.

The reference image is taken from the planning CT scan. Following this scan a digitally reconstructed radiograph will be produced of the reference treatment angles and these are then used as the standard reference images.

Each patient will have on-treatment imaging on days 1-3, day 9 and day 12.

For each patient and image fraction we will estimate the individual set up errors for the following parameters:

- 1 CLD- Central Lung Distance
- 2 CrLD- Cranial Lung Distance
- 3 CBESD Central Beam Edge Skin Distance
- 4 CIW Central Irradiated Width
- 5 CCD Cranio-Caudal Distance

For each individual patient (patient *i*) will estimate the individual mean set-up error,  $m_i$  and random set-up error  $\mathbb{Z}_i$ , set up errors for each of the parameters listed above.

For all patients in the support bra group we will calculate the overall population mean set-up error  $M_{pop}$  and the population systematic set-up error and the population random set-up error for each of the five parameters. We will also calculate 95% confidence intervals for the overall population mean set-up error  $M_{pop}$  and the population random set-up error. This will be repeated for patients in the control group.

We will then compare the study estimates of the population mean set-up error  $M_{pop}$  and the population random set-up parameters between the Support bra and control groups with a two independent samples *t* test. We will estimate a 95% confidence interval for the difference between the Support bra and control groups in these parameters for the five parameters from the two independent samples *t* test(36).

We will use this data from this pilot/feasibility study to inform the sample size calculation for the definitive RCT.

This information along with the acceptability of the study design and protocol to patients; patient recruitment and attrition/retention rates will enable us to determine whether or not the definitive RCT is feasible.

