	
 
Recruitment and attrition rates (CONSORT data): number of patients assessed for eligibility; reasons for exclusion, numbers discontinuing intervention (with reasons), numbers analysed and excluded from the analysis.
 
Number of missing values/incomplete cases: Acceptable rates of missing values for all the questionnaires prospectively defined as 0.5% in line with industry standards for phase I-III clinical trials.
 
Intervention adherence: Defined objectively as the number of radiotherapy fractions where the bra is used (for the intervention group) divided by the number of fractions prescribed.
 
Ease of radiation planning using the bra and ease (or difficulty) of producing an acceptable plan using the bra compared with no bra.
 
Intervention fidelity: During the study period site observations will be undertaken of treatment set-up for patients in both the control and intervention arms to ensure the support bra is used and positioned correctly and technique protocols are used in a standard manner across intervention and control groups. A checklist of criteria that reflects the protocol for using the support bra will be used to monitor intervention fidelity.
 
Feasibility of recruiting future participating centres.
 
Decision on primary endpoint for main trial.
 
	
	Primary Efficacy Endpoint Treatment accuracy and reproducibility will be collected as part of this feasibility trial. We would expect the S4A bra to either maintain or improve on existing levels of accuracy (where approximately 73.3% of cases had mean systematic errors <3mm and approximately 75% of cases had mean random errors <3mm for central lung depth on treatment verification images. Results will be viewed in relation to improvements in the dose to organs at risk (mean lung and mean heart dose where applicable).	
	
 
Secondary efficacy Endpoints
 
Skin reactions.
 
Dose to organs at risk.
 
Breast oedema.
 
Patient comfort.
 
Patient modesty.
 
Patient empowerment.
 
Participant views on acceptability of the intervention.
 
Therapist views on the acceptability of the intervention.
 
Body Image.
 
	

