## 1.0 Background

Breast cancer affects a substantial proportion of the population(6); with over 1.67 million women diagnosed globally in 2012(7). For many of these women the primary treatment is local excision (LE) followed by external beam radiotherapy to the whole breast. Traditionally this has been given using basic tangential radiotherapy beams. New technology employing complex approaches such as 3D conformal and Intensity Modulated Radiotherapy (IMRT) provide the opportunity to spare sensitive structures that lie close to the breast; these require greater accuracy in patient alignment. Set up inaccuracies (anterior-posterior and superior-inferior systematic displacements) have dosimetric consequences that vary depending on breast gradient, standard or IMRT based techniques and magnitude of error(8) and may increase the risk of a loco-regional recurrence(9) or a poorer cosmetic outcome (10). Added to this in the majority of radiotherapy centres worldwide women lie for breast irradiation, bare from the waist upwards, with up to four therapy radiographers (including men) adjusting and manipulating their thorax and breast in preparation for treatment. Most radiotherapy centres rely on the use of permanent tattoos marked on the patient and laser systems aligned to the machine. However, accuracy using this approach can be problematic(11) and the use of permanent tattoos is of concern to many patients(12). In addition, women with large (above a D bra cup size) or pendulous breasts can be difficult to position. Specifically, overhang of the breast inferiorly produces a self-bolusing effect that leads to an increased skin dose in the lower part of the breast and on the chest wall underneath the tissue overhang. The use of a support bra would lift the breast tissue away from the chest wall, reduce the skin reaction at the inferior aspect, making the potential cosmetic outcome and treatment experience for women with larger breasts more comparable to that experienced by women with smaller breasts

Currently no immobilisation device is available for use with supine positioning that can accurately stabilise the breast while also maintaining patient dignity(13). We have developed a support bra and determined proof of concept of the design through experimental testing.

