## 6.0 Randomisation

#### 6.1. Randomisation procedure

Prior to randomisation an eligibility checklist should be completed and signed informed consent should be obtained. Allocation will be through block randomisation (with blocks an integer multiple of four); stratified by breast/bra cup size (S4A bra size 3-7 vs. S4A bra size 8-12). The trial statistician will generate a randomisation schedule using existing software. This will be held remotely by the study-co-ordinator (who will not be directly involved in recruiting patients to the study). At the point of randomisation, the recruiting clinician will contact (telephone) the study co-ordinator, give the patient's details and NHS number and receive a study number and treatment allocation in return. At the end of the trial, the complete remote schedule will be checked against the study dataset. Staffing the randomisation line will be straightforward, as randomisation will occur exclusively during office hours.

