#### **6.2. Treatment Allocation**

Patients will be randomised 1:1 to receive the intervention (breast radiotherapy with S4A bra one tattoo) or the control (existing radiotherapy set-up with no immobilisation with tattoos).

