## 7.0 Trial Evaluations

#### 7.1. Accuracy and Reproducibility

Standard methods to calculate random and systematic errors will be used(33) taken from ontreatment imaging on days 1-3, then weekly until treatment completion. The random and systematic errors analysis will be reported with confidence intervals to allow estimation of the effect size for random and systematic errors (the probable primary endpoint for the definitive study) to check that the likely effect is within a clinically relevant range (as confirmation that it is worth progressing with the full trial). To check positioning patients in both arms of the study will have a single image taken at the start of the daily treatment exposure. This image will be used to confirm set up accuracy before the treated dose is delivered.

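### Randomisation is stratified by bra size but set-up error is compared by an unadjusted t test, so the interval is wider than the design warrants to the extent that bra size predicts set-up error

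*Protocol*

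**What the plan says.** Protocol 6.1 allocates patients in blocks, "stratified by breast/bra cup size (S4A bra size 3-7 vs. S4A bra size 8-12". Protocol 6.2 fixes equal allocation: "Patients will be randomised 1:1 to receive the intervention".

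Protocol 17.1 first derives a mean and a random set-up error for each patient on five image parameters. It then compares the mean set-up error and the "population random set-up parameters between the Support bra and control groups with a two independent samples" t test. The same test supplies the "95% confidence interval for the difference between the Support bra and control groups in these parameters". Bra size enters neither the test nor the interval, and no other section gives an adjusted between-arm analysis of set-up error.

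Three other statements bear on how much this matters:
- Section 17.0 says that the analysis will "focus on confidence interval estimation and not formal hypothesis testing".
- Section 7.1 says that the errors will be "reported with confidence intervals to allow estimation of the effect size for random and systematic errors", and calls them the probable primary endpoint of the definitive study. The Trial Summary lists accuracy and reproducibility as the primary efficacy endpoint.
- Section 1.0 remarks that "women with large (above a D bra cup size) or pendulous breasts can be difficult to position". Research question 4 (section 3.0 and Table 2) asks whether the bra positions all breast sizes equally well, and answers it by a separate correlation with breast volume.

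**The concern.** When allocation is blocked within strata, each arm receives nearly the same mix of bra sizes. Differences between strata then largely cancel in the difference between arms. A plain two-sample t test ignores this: its pooled SD still contains the between-stratum variation, so the standard error reflects a source of error that the design has removed. If bra size is related to set-up error, the interval is too wide and its coverage exceeds 95%.

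Interval estimation is the main product of this trial, and the number of patients is small. The interval for set-up error is to be used in judging whether the likely effect is large enough to justify the definitive trial, so avoidable width is worth removing when removal is nearly free. The method is written into the protocol, so it is not a detail left open for a statistical analysis plan.

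**Working it through.** **The plan's own figures.** Section 5.2 states that 40 patients estimate an SD to about ±23%. With 39 degrees of freedom, the chi-square 95% interval for an SD runs from 0.819s to 1.284s, an average half-width of (1.284 − 0.819)/2 = 0.23. The stated figure reproduces. Allowing for 20% attrition, 40/0.80 = 50, or 25 per arm, which also reproduces.

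**Inputs.** Evaluable patients per arm: 20 (section 5.2, after attrition) or 25 (all randomised). Allocation: 1:1 (6.2). Strata: two (6.1). Share of within-arm variance explained by the bra-size stratum, R²: not given in the document, so assumed to lie between 0 and 0.20.

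**Formulas.** The half-width of the 95% interval for the arm difference, in units of the total within-arm SD, with n per arm and N = 2n:
- unadjusted: t(0.975; N − 2) × √(2/n)
- adjusted for stratum: t(0.975; N − 3) × √(2/n) × √(1 − R²)

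**Numbers.** At n = 20 the unadjusted half-width is 2.024 × √(2/20) = 0.640 SD. At n = 25 it is 0.569 SD. The gain expressed as equivalent extra patients is 1/(1 − R²) − 1.

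| Assumed R² | Adjusted half-width, 20 per arm | Ratio to unadjusted, 20 per arm | Ratio, 25 per arm | Equivalent extra patients |
|---|---|---|---|---|
| 0 | 0.641 | 1.001 | 1.001 | 0% |
| 0.05 | 0.625 | 0.976 | 0.975 | 5% |
| 0.10 | 0.608 | 0.950 | 0.949 | 11% |
| 0.20 | 0.573 | 0.895 | 0.895 | 25% |

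So adjustment narrows the interval by 2.4%, 5.0% or 10.5% at R² of 0.05, 0.10 or 0.20. Put the other way, the unadjusted interval is 1/0.976, 1/0.950 or 1/0.895 times the adjusted one, which is 2.5%, 5.3% or 11.7% wider. At R² = 0 the adjusted interval is 0.1% wider, the price of one degree of freedom.

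**Simulation check.** 20,000 replicates were run with normal errors, arms balanced within two strata, N of 40 and 48, and strata split 50:50 and 30:70. At N = 40 with equal strata, the plain t interval covered 95.0%, 95.6%, 95.9% and 97.2% at R² of 0, 0.05, 0.10 and 0.20. The adjusted interval stayed near 95% throughout. The simulated ratios of mean width were 1.001, 0.974, 0.947 and 0.890, in line with the table. The other settings gave nearly the same results.

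**The case against.** The strongest objection is that the gain depends on a relation the protocol does not establish. Section 6.1 gives no reason for stratifying on bra size. The remark on difficult positioning in 1.0 leads straight into skin dose from tissue overhang, so skin reaction is an equally plausible reason. Eligibility already excludes the smaller cup sizes, which weakens any inference to a 3-7 versus 8-12 contrast. Research question 4 treats the size effect as unknown. All of this stands. A reader might infer that the planned interval is certainly too wide, but the document supports only the conditional statement.

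The second objection is that 17.1 compares two different quantities. Difficulty in positioning suggests more spread, not a shift in one direction. If only spread differs by size, an additive stratum term removes little from the signed mean error, and any benefit falls mainly on the random error. This stands too. Each patient's random error also rests on only the five images that 17.1 lists, and no stratum term can remove that measurement noise.

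The third is that little hangs on the result. The primary feasibility outcome is recruitment. The stop/go rule for accuracy in Table 1 uses the proportion of bra cases with errors above 3 mm, not the between-arm interval. The plain t interval is unbiased and errs on the cautious side. This limits the importance of the point but does not remove it, because 7.1 does use the intervals for an effect-size check.

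A reader might also infer that the raw SD would overstate the SD needed for the definitive trial. That follows only if the definitive trial adjusts for bra size, which the protocol does not say. The possible overstatement is also smaller than the ±23% uncertainty in the SD that the protocol itself accepts. Section 5.2 plans to combine the SD with published ones, and for that the raw SD may be the more comparable figure.

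**Conclusion.** The mismatch between 6.1 and 17.1 is real and is fixed in the protocol text. Its consequence is conditional and modest: intervals that adjustment would narrow by about 2%, 5% or 10-11% at an assumed R² of 0.05, 0.10 or 0.20, and no loss at R² = 0. These figures assume an additive stratum effect, equal variances and near balance of strata between arms. The document gives no value for R².

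The effect is lost precision with coverage above 95%. It is not bias, and nothing shows that it would lead to a wrong decision. The change is still worth making because almost nothing is lost if bra size proves irrelevant, while some precision is gained if it does not. Confidence is high in the mismatch and lower in the size of the gain. Extending the model to dose outcomes, or adding an arm-by-stratum term, is not needed for this point.

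**What to change.** In 17.1, replace the t test as the source of the between-arm estimate. For each of the five parameters, estimate the arm difference and its 95% confidence interval, for the patient-level mean and random set-up errors, from a linear model with arm and the bra-size stratum used at randomisation (3-7 versus 8-12). Report the residual SD from that model beside the raw SD, so that the definitive sample size can use whichever matches the analysis planned for that trial.

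The cost is about a sentence of protocol text and one degree of freedom. No new data are needed, because the stratum is known at randomisation. The per-arm summaries already described in 17.1 can stay as they are.

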### 17.2 Skin Toxicity

Skin toxicity will be measured using the Radiation Therapy Oncology Group (RTOG) toxicity scoring scale for acute skin reactions.

The following summaries will be presented: the number and percentages of patients reported as having an RTOG grade 1, 2 or 3 in each treatment arm as well as its associated 95% confidence interval; as well as the difference in skin reactions between each treatment arm and its associated 95% confidence interval for the difference(35). The incidence of dry or moist desquamation in the inframammary fold will also be recorded and compared between control and intervention arms.

## **18.0 Research Governance**

The study will be registered with the local R&D department and Sheffield Hallam University will act as the sponsor for the Trial. Three committees will be established to govern the conduct of this study: the Trial Steering Committee (TSC), an independent Data Monitoring and Ethics Committee (DMEC) and a Trial Management Group (TMG). The TSC will consist of a neutral chair with clinical and research expertise in radiotherapy, an independent radiographer and two patient representatives. The Committee will meet at 6 months from the start of the trial. The DMEC will consist of a statistician and 2 independent research radiographers with clinical trial expertise. Trial monitoring procedures and site monitoring will be undertaken at a level appropriate to a risk assessment performed by the sponsor or their delegate.

#### **19.2 Trial Steering Committee (TSC)**

The TSC will be made up of an independent chair, two patient representatives from our patient and public involvement group and an independent radiographer. The purpose of the TSC is to monitor progress of the trial and to ensure adherence to the protocol and the principles of Good Clinical Practice.

#### 19.3 Independent Data Monitoring and Ethics Committee (DMEC)

Members of the TMG will propose the DMEC membership and these will be subject to approval by the TSC. The purpose of this group is to monitor progress of the trial and they will be expected to meet at least once (in confidence) during the data collection phase of the trial to review outcomes, reporting these to the TSC where it is deemed appropriate to do so before the end of the trial period.

## **20.0 Trial Administration and Logistics**

#### **20.1. Protocol Compliance**

This clinical feasibility study will be conducted in accordance with Good Clinical Practice guidelines and the standards required by the Health and Social Care governance framework for England

#### **21.0 Patient Protection and Ethical Considerations**

Risks

The main risk with using a support bra is the potential to increase the surface (skin) dose that the patient receives compared to the skin dose they would experience if the bra were not used. To minimise this risk the bra has been designed using low attenuation materials and we have undertaken a series of experimental tests to assess the likely increase in surface dose. A graph showing the surface dose for no bra, the SuPPORT 4 All bra and thermoplastic material is presented in Appendix 2. Some centres currently use thermoplastic material to immobilise breast tissue. It is estimated using a single point dose measurement test that the SuPPORT 4 All bra increases the surface dose by approximately 6% compared with approximately 11% increase in surface dose when thermo-plastic material is used. An increase of 6% in surface dose is considered within a clinically acceptable spectrum and below that likely to be experienced for those women receiving radiotherapy to the breast at radiotherapy centres where thermoplastic immobilisation methods are employed.

For women in the intervention arm we propose to undertake two CT planning scans:

- 1. One scan with the S4A bra.
- 2. One scan without any immobilisation.

This extra CT scan will mean those women in the intervention arm will have an additional radiation exposure. The details of the additional radiation dose is defined below:

#### CT Planning control group (normal procedure of one CT scan for planning)

Calculated dose per procedure (ie one from control arm) is 7.2 mSv (Local DLP = 258 mGy.cm) (ImPACT CT Patient Dosimetry Calculator Version 1.0.4 27/05/2011 & confirmed by 'Doses to Critical Organs following Radiotherapy and concomitant imaging of Larynx and Breast', Harrison et al, BJR 80 (2007), 989-995).

#### **CT Planning Intervention Group**

Calculated dose per procedure (two procedures for the intervention arm ) is 7.2 mSv (Local DLP = 258 mGy.cm) (ImPACT CT Patient Dosimetry Calculator Version 1.0.4 27/05/2011 & confirmed by 'Doses to Critical Organs following Radiotherapy and concomitant imaging of Larynx and

Breast', Harrison et al, BJR 80 (2007), 989-995). Those in the intervention arm require two planning CT scans.

**Pre-Treatment Mega-voltage image- one procedure required for both control and intervention arm**: 4 Monitor Unit / image (Local Exposure) 0.6 mSv/MU (Doses to Critical Organs following Radiotherapy and concomitant imaging of Larynx and Breast, Harrison et al, BJR 80 (2007), 989-995).

On-treatment mega-voltage images delivered as part of the radiotherapy fraction no additional dose.

This study will recruit patients who will be receiving standard whole breast radiotherapy. Both arms of the study receive the same radiotherapy treatment. Therefore there is no additional risk arising from this element of standard of care treatment. Patients in the intervention arm (Arm B) receive 1 additional CT planning scan. This study requires exposures to ionising radiation which are detailed in sections 8-12 above. A small fraction of the total radiation dose required by the study is additional to routine clinical care, for Arm B only. The radiation dose for Arm A is identical to that for routine clinical care. Because the patients suitable for the study are generally larger, the breast dose for MV Verification is assumed to be higher as a consequence. For the purposes of ethical assessment this is estimated to be 4MU for the pre-treat MV image.

The total protocol dose for Arm A is 9.6 mSv and for Arm B is 16.8 mSv. This is equivalent to 4.2 and 7.3 years of average natural background radiation in the UK respectively.

Ionising radiation can cause cancer which manifests itself after many years or decades. The risk of developing cancer as a consequence of taking part in this study is estimated as 0.07 % for Arm A and 0.1% for Arm B. The additional risk to participants in Arm B is 0.04%. For comparison, the natural lifetime cancer incidence in the general population is about 50%.

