## **12.0 Treatment Verification**

Verification of the treatment fields is achieved using 2D megavoltage imaging in conjunction with radiographer assessment of the field coverage on the skin surface/bra surface in comparison with a 3D rendered image of the patient produced from the planning CT dataset. The megavoltage image is a pre-treatment beam portal image allowing assessment of central lung depth, lung symmetry and breast contour.

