## **12.1 Treatment Set-up Verification Breast**

The verification procedure outlined above is undertaken on fractions 1-3, then weekly, throughout the treatment course for the purposes of assessment of random and systematic error. All patients in the S4A study will have an image taken daily throughout the treatment course to reassure regarding breast positioning. The impact of the additional imaging is explained below:

- The effective dose from a single lateral portal image of 1 MU at 6MV is 0.6 mSv (Harrison et al BJR 2007 DOI: 10.1259/bjr/32814323). Where Sv represents Sievert (the SI unit for radiation absorption), 1Sv is roughly equivalent in biological effectiveness to 1Gy (1Gy is roughly equivalent to1000mSv). The maximum organ dose for 1 MU at 6MV is approximately 10 mGy.
- Five portal images received by patienrs not in the study will result in approximately 3mSv, fifteen portal images received by study patients will result in approximately 9mSv.

• The reported doses are for the particular patient model used in the reference quoted above, for the size of patient in the S4A study, there may be differences from the values quoted above.

All images are taken and assessed prior to treatment and a cine type time lapse image is taken on fraction 2 to provide additional information with regard to breathing motion. For purposes of assessing random and systematic error images from day 1 to 3 and then a weekly image will be used for both control and S4A intervention arms. The systematic error is calculated using the dataset from the first three images and adjustments made on fraction 4. On the first fraction the set-up is verified by the team of treating radiographers but also utilising the additional skills of the advanced practitioner in breast radiotherapy. Thereafter, images are reviewed online by the senior radiographer and further verified offline by a radiographer trained in portal image assessment. Tolerances used are 0.5cm on the central lung depth.

Measurements as determined by the OnTarget documentation will be recorded and assessed using the verification images as shown in Figure 1 below.

[figure not shown]

Figure 1 Measurement Parameters taken from on-treatment imaging.

- 1 CLD- Central Lung Distance
- 2 CrLD- Cranial Lung Distance
- 3 CBESD Central Beam Edge Skin Distance
- 4 CIW Central Irradiated Width
- 5 CCD Cranio-Caudal Distance

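### Section 21's radiation totals count one portal image and deny any extra dose in Arm A, while section 12.1 gives every study patient fifteen pre-treatment images against five outside the study

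*Protocol*

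**What the plan says.** Section 21.0 sets out the radiation exposure for ethical assessment. It counts one planning CT at 7.2 mSv in Arm A and two in Arm B. For each arm it adds one pre-treatment megavoltage image of 4 MU at 0.6 mSv per MU. The result is: "The total protocol dose for Arm A is 9.6 mSv and for Arm B is 16.8 mSv". These totals are then expressed as 4.2 and 7.3 years of natural background radiation, with cancer risks of 0.07% and 0.1%.

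Three sentences in the same place bear on what counts as extra:

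- On who receives extra dose: "A small fraction of the total radiation dose required by the study is additional to routine clinical care, for Arm B only"
- On images taken during the course: "On-treatment mega-voltage images delivered as part of the radiotherapy fraction no additional dose"
- On the control arm: "The radiation dose for Arm A is identical to that for routine clinical care"

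The imaging schedule is described elsewhere:

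- Section 7.1 gives patients in both arms one image each treatment day, used to confirm set-up before the treated dose is delivered.
- Section 12.0 defines the verification image: "The megavoltage image is a pre-treatment beam portal image allowing assessment of central lung depth".
- Section 12.1 states "All patients in the S4A study will have an image taken daily throughout the treatment course to reassure regarding breast positioning", introduces the dose figures with "The impact of the additional imaging is explained below", and says that all images are taken and assessed before treatment. It puts five images outside the study at about 3 mSv, and for the trial gives "fifteen portal images received by study patients will result in approximately 9mSv".

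**The concern.** The two sections cannot both be right. Section 12.1 treats ten of the fifteen images as additional to ordinary practice, in both arms, and gives them a dose. Section 21 includes one image, states that Arm A has no exposure beyond routine care, and limits the Arm B excess to one CT scan.

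Section 21 is where the protocol states total dose and risk for ethical assessment. Anyone relying on it would conclude that control patients receive no research exposure. That conclusion, the totals, the background-year equivalents and the cancer risks all rest on an image count that the protocol's own schedule contradicts.

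**Working it through.** **Inputs**

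- CT dose: 7.2 mSv per scan; one scan in Arm A, two in Arm B (section 21.0).
- Image dose: 0.6 mSv per MU (sections 12.1 and 21.0).
- MU per image: 1 in section 12.1; 4 in section 21.0, as an allowance for larger patients.
- Images: one in section 21.0; in section 12.1, fifteen for study patients and five outside the study.
- Fractions: 15 (section 8.1), which agrees with one image per day.

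**Formula**

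Total = (CT scans × 7.2) + (images × MU per image × 0.6) mSv

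**Step 1. Reproduce the stated totals (one image, 4 MU)**

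- Arm A: 7.2 + 4 × 0.6 = 9.6 mSv
- Arm B: 2 × 7.2 + 4 × 0.6 = 16.8 mSv

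Both match, so the sums are correct and the fault is in the inputs. The single image contributes 2.4 mSv, which is less than the 3 mSv that section 12.1 gives for the five images of routine care.

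**Step 2. Use section 12.1's count and dose (1 MU per image)**

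- Fifteen images: 15 × 0.6 = 9.0 mSv. Five images: 5 × 0.6 = 3.0 mSv. Both match section 12.1.
- Routine care: one CT plus five images = 7.2 + 3.0 = 10.2 mSv.

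| | Stated total | Total with 15 images | Excess over routine care | Excess implied by section 21 |
|---|---|---|---|---|
| Arm A | 9.6 | 7.2 + 9.0 = 16.2 | 16.2 − 10.2 = 6.0 | 0 |
| Arm B | 16.8 | 14.4 + 9.0 = 23.4 | 23.4 − 10.2 = 13.2 | 7.2 |

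(all in mSv)

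The stated totals are too low by 6.6/16.2 = 41% in Arm A and 6.6/23.4 = 28% in Arm B.

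**Step 3. Background-year equivalents**

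The protocol's figures imply 9.6/4.2 = 2.29 and 16.8/7.3 = 2.30 mSv per year. At 2.3 mSv per year, 16.2 mSv is about 7.0 years (stated 4.2) and 23.4 mSv is about 10.2 years (stated 7.3).

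**Step 4. Upper end, with 4 MU for every image (assumption)**

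- Fifteen images: 15 × 2.4 = 36.0 mSv. Five images: 5 × 2.4 = 12.0 mSv.
- Arm A: 7.2 + 36.0 = 43.2 mSv. Arm B: 14.4 + 36.0 = 50.4 mSv. Routine care: 7.2 + 12.0 = 19.2 mSv.
- Excess: 43.2 − 19.2 = 24.0 mSv in Arm A and 50.4 − 19.2 = 31.2 mSv in Arm B.

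**Step 5. Difference between arms**

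Arm B minus Arm A is 7.2 mSv (one CT) in every case.

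No cancer risk is recomputed here, because the protocol gives no risk coefficient and states its risks to one significant figure.

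**The case against.** The strongest defence is the sentence "On-treatment mega-voltage images delivered as part of the radiotherapy fraction no additional dose". The Trial Summary, Table 2 and section 17.1 all call the verification images on-treatment images. On that vocabulary section 21 is coherent by itself: one pre-treatment image is costed, and the rest are treated as part of the fraction. The protocol never says whether the image's monitor units are deducted from the prescribed fraction. Section 7.1's phrase placing the image at the start of the daily exposure could, taken alone, be read the same way.

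This does not remove the conflict. Section 12.0 defines the image as pre-treatment, section 7.1 goes on to say it is used before the dose is delivered, and section 12.1 calls the imaging additional and assigns it a separate dose. If the no-additional-dose sentence is meant to cover these images, it contradicts section 12.1 directly. It is unobjectionable only for images that really are part of the fraction, and the text should then say which those are.

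Other points stand in part:

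- The exposure is not concealed. Section 12.1 gives both counts and both doses, and section 21 refers readers back to sections 8 to 12.
- The difference in MU has a stated reason, and section 12.1 warns that its doses may differ for patients of the size in this study. Neither section applies 4 MU to the daily series, so the figures in step 4 show a range and are not evidence of error.
- The consent material is not shown, so nothing can be said about what participants were told.

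**Conclusion.** The concern holds. Section 21's totals leave out the daily imaging, and its statements that Arm A matches routine care and that extra dose falls on Arm B alone contradict section 12.1.

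The best-supported size uses section 12.1's own count and 1 MU per image: about 6 mSv of extra imaging dose in each arm, giving an excess over routine care of 6.0 mSv in Arm A and 13.2 mSv in Arm B. The size depends on the MU per image. That Arm A has an excess does not, since it appears on either basis.

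This is an error in the safety and ethics statement and should be fixed. It does not touch the endpoints, the sample size, the analysis or the stop/go criteria.

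**What to change.** 1. Settle the number of portal images and the MU per image once, and use the same values in sections 12.1 and 21.0.
2. Recompute section 21's total doses, background-year equivalents and cancer risks with the daily images included, and state the excess over routine care for each arm.
3. Correct the sentences that equate Arm A with routine care and confine the extra dose to Arm B. Correct the sentence on on-treatment images, or limit it to images shown to be part of the prescribed fraction.
4. Check that the participant information agrees with the revised figures.

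The cost is a recalculation by the medical physics expert and a text amendment, with no design change. The stated exposure becomes less favourable in both arms.
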